- Arm 2 (first 6 weeks): push notification reminders via OMRON Connect app on participant's phone to check BP and BP readings shared via OMRON app
- Start of week 7: Arms cross-over
- All participants:
 - o Personal dashboard with access to educational and social support resources
 - o Daily text message reminders and feedback for step count data
 - o Re-engagement protocol for low participation
 - o Weekly feedback on BP monitoring adherence

Outcome assessments (end of 12 weeks)

- Primary outcome assessments of adoption, adherence, and acceptability
- Secondary outcome assessments of effectiveness and reach

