6.1 Primary Endpoints

The RE-AIM framework, which focuses on five dimensions (reach, effectiveness, adoption, implementation and maintenance), considered to be important for behavioral health interventions will guide the evaluation for the primary endpoints of feasibility of the SMART-HABITS program.

- 1) Adoption: a) participant retention rate at 4, 8, and 12 weeks, b) Percentage of participants who used SMART-HABITS at any point during the 12 weeks.
- 2) Adherence: a) percentage of self-monitored BP transmissions performed out of the recommended and b) percentage of step count data transmissions out of the recommended.
- 3) Acceptability: a) improvement of the pre- and post-study scores on the attitudes toward mHealth questionnaire, b) satisfactory ratings on the ease of use survey during the study and at the end of the study and, c) interview feedback after the end of the pilot study.

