6.2 Secondary Endpoints

The secondary measures of effectiveness will include: a) change in pre-pilot and post-pilot questionnaire scores regarding CKD knowledge, self-efficacy, self-management, eHealth literacy and disease-related quality of life; b) change in baseline BP (as determined by the first BP measure transmitted) compared to mean BP after 4, 8, and 12 weeks, and c) change in mean step count in first week compared to mean step count after 4, 8, and 12 weeks.

An additional endpoint includes an assessment of “Reach”, which will be the number and characteristics of participants enrolled in the study.

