6.3 Statistical Methods

We will describe the study population with mean values (standard deviations) or medians and quartiles as appropriate for continuous variables and percentages for categorical variables using STATA software. Specifically, we will report the enrollment rate, the retention rate, and participant ratings on ease of use surveys. We will explore if these characteristics differ by age, gender, and education level with analysis of variance and Pearson's Chi2-testing. We will report the adoption as the percentage of participant still enrolled in the intervention at 4, 8, and 12 weeks and the percentage of participants who used SMART-HABITS at any point during the 12 weeks of the pilot trial. We will report the percentage of the self-monitored BP transmissions performed out of the recommended and also the percentage of the step count data transmissions out the recommended during the pilot trial.

We will perform an exploratory analysis of the change in 1) pre- and post-trial questionnaire scores, and 2) baseline BP and first week mean step count compared to the mean BP and step counts after 4, 8, and 12 weeks using paired t-tests, recognizing that over time the amount of information will diminish as we anticipate fall out, but also, a longer time for the intervention to have an effect. We will explore the association of baseline questionnaire scores with adoption and adherence with linear regression models adjusted for age, sex, race, and education. These will be exploratory analyses since the study was not powered to detect a statistically significant difference. We hypothesize that higher adherence and adoption will be associated with increased scores on baseline measures of self-efficacy, attitude toward mHealth, and self-management. We will also explore for trends in adherence with generalized linear mixed effects models and if blood pressure control or amount of steps modifies trend in adherence.

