7.1 Description

The intervention will utilize the Way to Health platform to provide: a) text message reminders, b) text message tailored feedback in response to transmitted data on blood pressure (in the text message arm) and daily step counts, c) positive affirmation text messages sent throughout the study to encourage behavior participation, d) provide links to educational resources, including a video on demonstrating how to correctly perform blood pressure self-mentoring in the portal, e) provide links to community resources and CKD patient forums within the portal, and the f) option to select a accountability partner to share the participant's reminders and feedback. The intervention was developed using a theory-based, and evidence-based approach.

Study Protocol: Supporting Self-Management of Healthy Behaviors (SMART-HABITS)

The Way to Health platform is an automated information technology platform that integrates wireless devices, clinical trial randomization and enrollment processes, messaging (text, e-mail, voice), self-administered surveys, and secure data capture for research purposes.^{141,142} Way to Health has been used in prior behavior intervention studies.¹⁴³⁻¹⁴⁶

At enrollment, a questionnaire (see Appendix IV) will be completed by all participants to capture demographics, kidney disease knowledge, ability to manage kidney disease, confidence in managing kidney disease, opinions of and ability to use mobile health technology. At enrollment, participants will complete a patient-generated “action plan” (questions in Appendix IV) in order to set realistic goals and encourage participants to create goals that involve positive action- with the minimum targets. Participants will develop short-term goals to help initiate changes and achieve success.

Participants will be asked to check their BP at least three times per week and then to communicate these BP readings with the research team using text message or with the OMRON Connect app (depending on the phase- please see below), and upon receipt, the participants will then receive tailored feedback.

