 - Participants randomized in Phase 1 to the OMRON Connect App arm will complete the same survey questions as those in the Texting Arm. Participants using the OMRON connect app will also receive reminder messages on a similar frequency as the texting arm and will also be customized the participant's schedule as they can choose which days and times to receive push notification reminders delivered by the OMRON connect app. Upon receipt of the BP reading, participants will receive similar BP feedback (Appendix VII).
- Phase 2 (weeks 7-12):
 - At the conclusion of week 6, individuals will “crossover” to the opposite study arm and will continue in the study for an additional 6 weeks using the opposite technology to communicate their BP readings.

Motivating and positive affirmation messages will be sent to participants on a weekly basis (Appendix VII). After 4 weeks,

Study Protocol: Supporting Self-Management of Healthy Behaviors (SMART-HABITS)

and 8 weeks of the intervention, a usability survey (Appendix V) will be sent out to assess the ease of use of SMART-HABITS. Automated messages will be sent at key milestones to promote adherence to study procedures. Weekly feedback will be sent the morning after the end of the week. Daily feedback on performance from the prior day will be sent each morning.

Within SMART-HABITS' smartphone web-based application, there will be a portal which provides:

- Educational information that incorporates both clinical and lay-experiential CKD knowledge: Educational resources will present the health-related benefits of self-monitoring, reducing blood pressure, and increasing physical activity. Positive expectations will be outlined by ways that use self-monitoring BP and increasing physical activity may reduce the chances of experiencing negative health consequences.
- Graphical displays of personally set goals and real-time progress to goals
- Web links to social support

Throughout the study, if participants are identified to have low engagement with the intervention, identified through remote monitoring and defined as no BP readings for >1 week or no step counts in 4 days, they will undergo a re-engagement protocol. The re-engagement protocol includes the research team contacting participants with text messages to re-engage them and if after two attempts, the participant continues to not be engaged, they will be called and interviewed over the phone to provide more granular information to assess real-time barriers.

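### The paired t-tests for BP and step change at 4, 8 and 12 weeks allow for fall-out as lost information but not as selective loss

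*Combined protocol and SAP*

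**What the plan says.** Section 6.3 of the combined protocol and SAP tests change from the starting values of BP (baseline) and steps (first-week mean), which are to be "compared to the mean BP and step counts after 4, 8, and 12 weeks using paired t-tests, recognizing that over time". The plan then concedes that fewer data will remain later: "the amount of information will diminish as we anticipate fall out". It adds that later time points allow longer for an effect to appear.

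Section 6.2 defines the BP measure as "change in baseline BP (as determined by the first BP measure transmitted) compared to mean BP after 4, 8, and 12 weeks". Steps are handled in parallel, with the first-week mean as baseline. No averaging window is given for the later values.

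Other provisions bear on loss:
- Section 6.1 reports "participant retention rate at 4, 8, and 12 weeks" as a feasibility endpoint.
- Section 7.1 says that when participants show low engagement, "they will undergo a re-engagement protocol".
- Section 4.4 offers those who want to stop the option of self-monitoring only, instead of full withdrawal. It does not say whether their readings are analysed.
- Section 9.5 enrols more patients if 20% are lost.

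Section 6.3 does plan mixed models, but with adherence as the outcome. No missing-data method, analysis population or sensitivity analysis is given for BP or step change. Sections 5.2 and 6.3 call these analyses exploratory and unpowered.

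**The concern.** A paired t-test needs both values from the same person. Read as time-point means, the week-4, week-8 and week-12 tests therefore use three successively smaller groups. A difference between the week-4 and week-12 results could reflect who stayed as much as what changed. Acknowledging that information diminishes covers wider intervals; it does not cover selection.

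Selection is plausible here, though not shown. Participants send the outcome data themselves, so disengaging and having a missing outcome are the same event. They also receive feedback on BP and steps, so they see their progress before deciding whether to continue. Section 6.3 itself plans to explore whether BP control or step count modifies the trend in adherence.

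At stake is the answer to two research questions in section 2: whether BP control changes, and how well step goals are met. The primary feasibility endpoints are not affected.

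**Working it through.** The plan gives no SD, effect size, alpha or dropout rate for these tests, so there is no figure of its own to reproduce. What follows is illustration under stated assumptions.

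**Inputs from the documents.** n = 40 (section 3.3.1). Time points are 4, 8 and 12 weeks (section 6.2). The only loss figure is 20% (section 9.5), which is a trigger for more enrolment and not a forecast.

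**1. Identity.** If a share p is lost, the full-cohort mean is (1 − p) × stayers + p × leavers. The error of the stayers' mean is therefore p × (stayers' mean change − leavers' mean change). At p = 0.20, a gap of 5, 10 or 15 mmHg gives an error of 1, 2 or 3 mmHg. No gap gives no error.

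**2. Four-visit BP simulation (all assumed).** True change is 0, baseline SD 12, SD of underlying 12-week change 8, residual SD 5 and two-sided alpha 0.05. Dropout after weeks 4 and 8 depends on observed change. With 20% loss, n is about 40, 36 and 32. There were 3,000 trials per row, with a Monte Carlo SE of 0.034 for the paired error.

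| Log-odds of leaving per mmHg of change | Paired week-12 error (mmHg) | Mixed-model error (mmHg) |
|---|---|---|
| +0.10 (non-improvers leave) | −1.11 | 0.00 |
| +0.05 | −0.59 | +0.01 |
| 0 (unrelated) | +0.01 | +0.01 |
| −0.05 | +0.59 | +0.01 |
| −0.10 (improvers leave) | +1.11 | 0.00 |

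A log-odds of 0.10 means that a change 10 mmHg worse multiplies the odds of leaving by exp(1.0) = 2.7. At 0.02 the multiplier is exp(0.2) = 1.22 and the paired error is −0.23. By the identity, an error of 1.1 at 20% loss corresponds to a stayer–leaver gap of 1.1 / 0.20 = 5.5 mmHg.

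**3. Precision.** The CI half-width is t(0.975, n − 1)/√n × SD of change. For n = 32 that is 0.361 × √(8² + 5² + 5²) = 0.361 × 10.7 = 3.9 mmHg; the simulated average is 3.7 to 3.8. The model loses no precision: its estimator SD is 1.79 to 1.83, against 1.84 to 1.89 for the paired test.

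**4. Sensitivity to the assumptions.**
- With 10–30% loss and change SD 5–10, at log-odds 0.10 either way, the paired error is 0.5 to 1.7 mmHg.
- With 50 enrolled and the same 20% loss (40 remaining), the error at +0.10 is −1.10. Extra enrolment restores numbers but leaves the bias.
- With a different structure (SD 15, within-person correlation 0.6, nominal 20% dropout), the error is −1.1 under moderate and −2.4 under strong dependence. Rejection of a true null is 7.1% and 15.0%.

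**5. Averaging window.** This uses a weekly stream of three readings, with a single first reading as baseline and log-odds 0.10 either way. The error is about 1.05 mmHg if week 12 alone is averaged, 0.6 for weeks 9–12, and 0.1 for a cumulative mean over weeks 1–12, which is a different quantity. With residual SD 10 per reading these become 2.3, 1.6 and 0.1.

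**6. Model with windows of weeks 3–4, 7–8 and 11–12.** These are results at log-odds +0.10 / −0.10.

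| Residual SD | Paired error | Model error |
|---|---|---|
| 5 | −0.85 / +0.91 | −0.10 / +0.18 |
| 10 | −1.98 / +2.14 | −0.22 / +0.36 |

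**7. Dropout driven by the next, unobserved BP (four-visit set-up).** The paired error is −1.67 / +1.72 and the model error −0.83 / +0.89. Since 0.83/1.67 = 0.50 and 0.89/1.72 = 0.52, about half the bias remains.

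**8. Steps (assumed).** Between-person SD is 2,500, change SD 1,500, residual SD 800, log-odds 0.5–1.0 per 1,000 steps, and loss 20%. The paired error is +189 to +312 steps/day if non-improvers leave, −166 to −296 if improvers leave, and +11 if unrelated (Monte Carlo SE about 8). The model error is +8 to +12. The CI half-width is about 640 to 670.

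**The case against.** The strongest reply is that nothing rests on these tests. The study is a feasibility pilot, no sample size was computed, and efficacy is secondary or exploratory. Both sequences receive the program throughout, so the pre-post change is uncontrolled and, for BP, starts from a single reading. Removing about 1 mmHg of possible attrition bias does not turn it into an effect estimate. This stands, and it limits the weight of the point. It does not justify leaving an avoidable bias where the remedy is cheap.

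The plan also does not ignore loss. It acknowledges fall-out in the same sentence, reports retention at the same time points, tries to re-engage participants, and lets leavers keep monitoring. These steps may reduce the loss and will make it visible. None of them adjusts the BP or step estimates.

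The sizes above are assumed, and the four-visit errors at 20% loss are under a third of the CI half-width. That also stands. The shrinking-group reading itself depends on an undefined window, although the fall-out wording fits time-point means better than a cumulative mean.

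A reader might infer that the change of reporting route ("Start of week 7: Arms cross-over") adds a material bias, because baseline and later BP values arrive by different routes. The documents do not support that. Participants use one OMRON cuff throughout, the feedback is described as similar, and no text/app difference in BP is given. Any such difference would also cancel in the paired mean while both arms keep equal numbers.

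**Conclusion.** The point holds as a modest one. Section 6.3 has no means of handling selective loss in the BP and step comparisons, and a better method is available from data already collected. Under the assumed inputs at 20% loss, the week-12 BP error is about 0.2 to 1.1 mmHg either way. It is zero if dropout is unrelated to BP change, and about 0.1 if a cumulative mean is intended. Stronger dependence, heavier loss or noisier readings would make it larger.

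Two stronger readings should be resisted. One is that the plan will overstate benefit: the documents do not say who leaves, and if improvers leave the error runs the other way. The other is that a mixed model removes the problem: its near-zero error in the four-visit simulation arises because dropout there depends only on values the model sees.

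**What to change.** In section 6.3, replace the paired t-tests for BP and steps with the following.

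- **Model.** Fit one linear mixed model per outcome, with baseline in the outcome vector, categorical time, an unstructured covariance and a small-sample correction such as Kenward-Roger. That correction was not itself run. A t test on completers − 1 df, used as a stand-in, rejected a true null in 4.7–5.3% of trials, against 5.7–6.3% for a normal test.
- **Data.** Use all available readings, and say explicitly that this includes participants who continue with self-monitoring only (section 4.4).
- **Window.** State an averaging window for each time point that does not straddle the week-7 switch, for example weeks 3–4, 7–8 and 11–12. Section 7.1 says "Participants will be asked to check their BP at least three times per week", so each two-week window has at least 2 × 3 = 6 requested readings.
- **Reporting.** Give the change with its 95% CI and n at each time point. Keep the paired results as a sensitivity display.
- **Optional.** A covariate for current reporting technology in the BP model.

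The cost is a few sentences and a few lines of Stata. Mixed models are already planned for adherence, and the readings and their dates are already collected. The downside is the missing-at-random assumption. With the example windows an error of about 0.1 to 0.4 mmHg remains (paired test: 0.9 to 2.1), and about half the bias remains if dropout follows unobserved values.

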6.4 Sample Size and Power

The primary purpose of the pilot trial is to assess for acceptance and feasibility of a patient-centered mHealth self-management support intervention. Therefore, no sample size was formally computed.

7. Study Intervention

7.1 Description

The intervention will utilize the Way to Health platform to provide: a) text message reminders, b) text message tailored feedback in response to transmitted data on blood pressure (in the text message arm) and daily step counts, c) positive affirmation text messages sent throughout the study to encourage behavior participation, d) provide links to educational resources, including a video on demonstrating how to correctly perform blood pressure self-mentoring in the portal, e) provide links to community resources and CKD patient forums within the portal, and the f) option to select a accountability partner to share the participant's reminders and feedback. The intervention was developed using a theory-based, and evidence-based approach.

Study Protocol: Supporting Self-Management of Healthy Behaviors (SMART-HABITS)

The Way to Health platform is an automated information technology platform that integrates wireless devices, clinical trial randomization and enrollment processes, messaging (text, e-mail, voice), self-administered surveys, and secure data capture for research purposes.^{141,142} Way to Health has been used in prior behavior intervention studies.¹⁴³⁻¹⁴⁶

At enrollment, a questionnaire (see Appendix IV) will be completed by all participants to capture demographics, kidney disease knowledge, ability to manage kidney disease, confidence in managing kidney disease, opinions of and ability to use mobile health technology. At enrollment, participants will complete a patient-generated “action plan” (questions in Appendix IV) in order to set realistic goals and encourage participants to create goals that involve positive action- with the minimum targets. Participants will develop short-term goals to help initiate changes and achieve success.

Participants will be asked to check their BP at least three times per week and then to communicate these BP readings with the research team using text message or with the OMRON Connect app (depending on the phase- please see below), and upon receipt, the participants will then receive tailored feedback.

Participants will be asked to set a daily step goal of at least 3,000 steps per day at the start of the study and transmit their step count information to the research team on a daily basis. By providing a minimum threshold puts more emphasis on encouraging more sedentary individuals to walk more and less emphasis on getting highly active individuals to be more active. Participants will be reminded once a day in the evening to sync their steps with the FitBit app in order to transmit them to the Way to Health platform. Participants will receive daily individual performance feedback on their steps from the previous day. Participants will later be sent messages to see if they would like to increase their daily step goal.

Participants will be instructed how to correctly undertake BP self-monitoring to promote self-efficacy through a demonstration video available on Way to Health. Participants will be asked to rehearse self-monitoring at the initial study visit via a secure video-based platform using Zoom.

- Phase 1 (weeks 1-6):
 - After consenting to participate in the study, participants will be randomized to start with Texting (Arm 1) or the OMRON Connect App (Arm 2) to communicate BP readings.
 - Each arm will receive specific instructions pertinent to the specific phase tasks - available as a google document and will also be mailed at the beginning of the study (Appendix II).
 - Participants randomized to the texting arm in Phase 1 will receive automated text message reminders to check their BP on a personalized basis (minimum of three days per which) as participants will choose which days and times to receive these reminders at the beginning of the study. Participants will then transmit the BP readings with text message to the secure Way to Health server. If a blood pressure reading is not received within 3 hours, another reminder will be sent. Automated text message feedback will be sent after the BP reading is recorded with a tailored message regarding any further required actions based upon the BP readings obtained. Any participant with a single systolic blood pressure reading >200mmHg or two consecutive systolic blood pressure readings >180 mmHg or diastolic blood pressure readings >110 mmHg will be contacted immediately by an MD ([name]) for assessment (including evaluation for symptoms of hypertensive emergency) and referral to the emergency department, if indicated. Please see full text message algorithm (Appendix VII).
 - Participants randomized in Phase 1 to the OMRON Connect App arm will complete the same survey questions as those in the Texting Arm. Participants using the OMRON connect app will also receive reminder messages on a similar frequency as the texting arm and will also be customized the participant's schedule as they can choose which days and times to receive push notification reminders delivered by the OMRON connect app. Upon receipt of the BP reading, participants will receive similar BP feedback (Appendix VII).
- Phase 2 (weeks 7-12):
 - At the conclusion of week 6, individuals will “crossover” to the opposite study arm and will continue in the study for an additional 6 weeks using the opposite technology to communicate their BP readings.

Motivating and positive affirmation messages will be sent to participants on a weekly basis (Appendix VII). After 4 weeks,

Study Protocol: Supporting Self-Management of Healthy Behaviors (SMART-HABITS)

and 8 weeks of the intervention, a usability survey (Appendix V) will be sent out to assess the ease of use of SMART-HABITS. Automated messages will be sent at key milestones to promote adherence to study procedures. Weekly feedback will be sent the morning after the end of the week. Daily feedback on performance from the prior day will be sent each morning.

Within SMART-HABITS' smartphone web-based application, there will be a portal which provides:

- Educational information that incorporates both clinical and lay-experiential CKD knowledge: Educational resources will present the health-related benefits of self-monitoring, reducing blood pressure, and increasing physical activity. Positive expectations will be outlined by ways that use self-monitoring BP and increasing physical activity may reduce the chances of experiencing negative health consequences.
- Graphical displays of personally set goals and real-time progress to goals
- Web links to social support

Throughout the study, if participants are identified to have low engagement with the intervention, identified through remote monitoring and defined as no BP readings for >1 week or no step counts in 4 days, they will undergo a re-engagement protocol. The re-engagement protocol includes the research team contacting participants with text messages to re-engage them and if after two attempts, the participant continues to not be engaged, they will be called and interviewed over the phone to provide more granular information to assess real-time barriers.

8. Safety Management

There will only be direct contact with human subjects if they are given the wearable devices in person but this would only be done so in a socially distanced fashion (at least 6 feet apart) and with appropriate face coverings. There will be an intervention delivered by health information technology to help encourage healthy behaviors. The potential risk posed by study participation remains minimal, as the intervention is simply text reminders and collection of data from self-monitoring of blood pressure and physical activity via remote devices. According to the Food and Drug Administration (FDA) guidance, the Way to Health research platform, Fitbit and OMRON blood pressure machine wearable devices would be considered general wellness products since they meet the following two factors: (1) intended use that relates to maintaining or encouraging a general safety of health or a healthy activity or an intended use that relates the role of healthy lifestyle with helping to reduce the risk or impact of certain chronic disease or conditions (e.g., weight management, blood pressure management, physical fitness, self-esteem), and (2) present a low risk to the safety of users and other persons since the mHealth technology and wearable device are not invasive, are not implants, and do not involve an intervention or technology that may pose a risk to the safety of users and other persons if specific regulatory controls are applied (e.g., lasers or radiation exposure). General wellness products may include software programs and other products that are commonly, though not exclusively, available from retail establishments. A mobile application or wearable device that solely monitors and records physical activity or blood pressure might present a risk of inaccuracy, but the technology does not pose a risk to the safety of users and others persons if specific regulatory controls are not applied. Additionally, a mobile technology that reminds users of measures to reduce a medical condition or increase health does not pose a risk to the safety of users and others persons if specific regulatory controls are applied. Since we have access to participants smartphones, there is potential loss of confidentiality. Additionally, the risks posed by blood pressure monitoring, and participating in general wellness, such as increasing physical activity poses no greater risk than if not participating in study or usual care. Additionally, the health behavior interventions delivered through Way to Health have been shown to be safe.

Additionally, this study will include the following data and safety monitoring plan.

Purpose: The data and safety-monitoring plan is written to ensure the safety of participants and verify the validity and integrity of the data. This monitoring plan details the source data verification of intervention, safety parameters, and the frequency of monitoring and regulatory document review.

Risk of Study: The study incurs minimal risk because the Way to Health research platform has proven to be safe in multiple prior behavioral health intervention studies, the technology and devices used in the feasibility trial are considered by the FDA to be general wellness products, and the real risk is to confidentiality.

Responsible Parties of Monitoring

1. Principal investigator: The PI will regularly monitor the data in collaboration with the research team.

Study Protocol: Supporting Self-Management of Healthy Behaviors (SMART-HABITS)

The PI will also be responsible for ensuring all source documentation exists for the data and all corrections are done according to the principles of Good Clinical Practice.

2. IRB: periodic review by the University of Pennsylvania's IRB.

3. Research Assistant (RA): during the course of the study, safety and data quality monitoring will be performed on an ongoing basis by the RA, in addition to the PI. The RA will be responsible for monitoring all data collected.

Ongoing Monitoring Meeting: monitoring days will be conducted periodically throughout the study; beginning no later than 2 weeks after the first participant is enrolled. Subsequent monitoring meetings will be every four weeks.

Assessing Adverse Events: Monitoring for adverse events will be conducted by the PI, [name], and the RA.

Participants will be asked an open-ended question via Way to Health to assess if participants are experiencing any medical concerns related to their participation in the study.

Reporting Events: Any side effects of notable medical concerns will be reported to the PI to determine a course of action.

Any adverse effect will be reviewed by [name] and [name] (primary mentor). After removal of identification information, all serious adverse events will be reported to the University of Pennsylvania IRB and the funding agency within 24 hours. All adverse events will be recorded and a summary table reviewed by the IRB annually.

Data, Safety, and Monitoring Report: The PI will provide a summary of the DSM report on an annual basis as part of the progress report. The DSM report will include the expected versus actual recruitment rates, retention rates, any quality assurance and regulatory issues that occurring during the past year, summary of adverse events, and any actions or changes with respect to the protocol. Copies of each report and documentation of IRB notation and receipt will be kept in the PI's study file.

9. Study Administration

